Exploratory Aim 6: Explore the effects of cortisol on resting state functional connectivity using whole brain connectomic mapping.

Exploratory Aim 7: Explore the impact of depressive symptoms on memory and hippocampal structure, activation, connectivity and 1HMRSS outcomes in response to hydrocortisone administration.

2. Background.

- Describe past experimental and/or clinical findings leading to the formulation of your study.
- For research involving investigational drugs, describe the previously conducted animal and human studies.
- For research that involves FDA approved drugs or devices, describe the FDA approved uses of this drug/device in relation to your protocol.
- Attach a copy of the approved labeling as a product package insert or from the Physician's Desk Reference.

You may reference sponsor's full protocol or grant application (section number and/or title) or if none, ensure background includes references.

Please respond to all components of this item, or clearly indicate which components are not applicable.

a. Background

See grant application uploaded in section 4.1.3d of the Smartform. The background information can be found in Section 3 (Research Strategy, pages 68-69).

b. Current practice

N/A

3. Study Design.

Describe the study design (e.g., single/double blind, parallel, crossover, etc.) Consider inserting a scheme to visually present the study design.

The study involves a double-blind, placebo-controlled, crossover design of hydrocortisone in depressed and non-depressed (healthy controls) participants. Within each group (depressed and non-depressed), participants will be randomized to receive

Form A

IRB # STU 2018-0360

hydrocortisone or placebo for 3 days, followed by MRI and cognitive testing on day 3. Participants will then undergo a 25-day washout of study medication and will then, again, receive hydrocortisone or placebo for 3 days, followed by MRI and cognitive testing. The order in which participants will receive hydrocortisone vs. placebo will be randomized by a study statistician.

4. Research Plan / Description of the Research Methods:

4.a. Provide a **comprehensive narrative** describing the **research methods**.

- 1) Provide the **order in which tests/procedures will be performed**,
- 2) Provide the **setting** for these events and a description of the **methods used to protect privacy** during the study.
- 3) Provide the **plan for data analysis** (include as applicable the **sample size calculation**)

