Please respond to all components of this item, or clearly indicate which components are not applicable.

Informed consent and all study procedures, other than neuroimaging, will be conducted at BL8.224 or remotely through secure video conferencing software (e.g. Zoom, Teams). Neuroimaging will be done at the AIRC. When informed consent is conducted remotely, DocuSign will be used to obtain signatures. Please see the next page for the assessment schedule.

Methods used to protect privacy: Deidentified data will be stored in REDCap – a self-managed, secure, web-based solution that is designed to support data collection strategies for research studies. Only researchers associated with the study will have access to any protected health information (PHI). This information will not be stored on REDCap. Identifying information will be kept in a separate password-protected file only accessible to the PI and the research team on a need-to-know basis. Data will be analyzed by group, and subjects will be identified only by a subject ID number to protect their confidentiality. Researchers will destroy the personal identifiers upon completion of data collection for the study.

Data analysis plan:

Aim 1: Determine the effect of cortisol on task-driven hippocampal activation using, for the first time, high-resolution (1.5 mm isotropic) fMRI of hippocampal subfields (i.e., DG/CA3, CA1, subiculum). The design is a two-period crossover with randomized order of treatment conditions, and the primary interest is in the treatment effect on hippocampal subfield activation, estimated as the within-subjects difference in hippocampal subfield activation between the hydrocortisone and placebo treatment conditions. The index of hippocampal subfield activation is a beta-weight of the contrast of the task-active condition vs. the control condition (e.g. novel vs. familiar in the Novelty Detection task and lure correct rejections vs. false alarms in the Mnemonic Discrimination task). We will use linear mixed effects regression to estimate the following model of DG/CA3 activation, Y_{ijk} , of the i^{th} subject in the j^{th} group in the k^{th} period, cast in a traditional longitudinal data setup.

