$Y_{ijk} = \mu_i + \beta_c C_{ijk} + \gamma_t T_k + \gamma_c (C_{ijk} - C_{ij0}) + \varepsilon_{ijk}$, where the subject-level mean $\mu_i = \mu + S_i$ is comprised of an overall mean μ and a random subject effect S_i , the time and treatment condition indicators are T_k and C_{ijk} , and ε_{ijk} represents a random residual effect. The corresponding between-subjects sub-model is $Y_{ij0} = \mu_i + \beta_c C_{ij0} + \varepsilon_{ij0}$, where the parameter β_c is identified with the initial condition assignment, which is synonymous with group assignment and therefore represents the carry-over effect. The corresponding within-subjects sub-model is $\Delta Y_{ij} = Y_{ij1} - Y_{ij0} = \gamma_t + \gamma_c (C_{ijk} - C_{ij0}) + (\varepsilon_{ij1} - \varepsilon_{ij0})$, where the parameter γ_c is identified with the change in assigned condition and therefore represents the treatment effect.

Aim 2: Determine the effect of cortisol on hippocampal subfield volume using high-resolution structural MRI. Using the same randomized regression approach described above we will assess mechanistic aim 2.

Aim 3: Assess changes in hippocampal NAA, Glu, Cho and ml with cortisol using ^1HMR S. Similarly, changes in spectroscopy will be assessed using the randomized regression utilized in the previous aims.

Aim 4: Determine the effect of cortisol on declarative and visuospatial memory. We will estimate the treatment effects on declarative memory using the same linear mixed model setup as the primary aim.

Aim 5: Examine whether sex, stress, early life adversity, age, physical activity, GCR number or sensitivity, or changes in sleep during cortisol administration, predict hippocampal CS response, as assessed by memory testing and neuroimaging. We will assess treatment moderation by sex, stress, early life adversity, age, physical activity, and changes in sleep using the modeling setup described in the primary aim with additional terms added to the model. To assess the moderation of a dichotomous variable (i.e., sex), a group indicator (male vs. female) will be added to the regression model (

Form A

IRB # STU 2018-0360

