$Y_{ijk} = \mu_i + \beta_c C_{ij0} + \gamma_t T_k + (\gamma_c + \gamma_{cf} F_i)(C_{ijk} - C_{ij0}) + \varepsilon_{ijk}$, where the overall treatment effect $\gamma_c + \gamma_{cf} F_i$ is allowed to depend on an indicator F_i of sex. For continuous variables, baseline levels will replace the indicator of sex. Continuous moderator analyses will be refined entering and, adjusting for changes in moderators over time by including baseline and longitudinal levels in the model as

$Y_{ijk} = \mu_i + \beta_c C_{ij0} + \beta_q Q_{ij0} + \gamma_t T_k + (\gamma_c + \gamma_{cq} Q_{ij0})(C_{ijk} - C_{ij0}) + \gamma_q (Q_{ijk} - Q_{ij0}) + \varepsilon_{ijk}$. Here, the overall treatment effect $\gamma_c + \gamma_{cq} Q_{ij0}$ is allowed to depend on baseline levels, and the term $\gamma_q (Q_{ijk} - Q_{ij0})$ adjusts for changes from baseline in the within-subjects sub-model.

Aim 6: Explore the effects of cortisol on resting state regional functional connectivity, and whole brain connectomics.

As discussed in the primary aim, the treatment effects on resting state functional connectivity will be assessed using a randomized regression in a traditional longitudinal cast. The key indices of interest will be overall measures of network integrity (e.g., degree, centrality, rich club architecture, etc.).

Aim 7: Explore the impact of depressive symptoms on memory and hippocampal structure, activation, connectivity and 1HMRS outcomes in response to hydrocortisone administration. Depression as a moderator will be assessed similarly to the moderators proposed in aim 5. However, a dichotomous indicator variable representing baseline group assignment (depressed vs. healthy control) will also be included in the model.

Sample size determination:

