
Aims 5 and 7: Complete data from 48 participants (50% women) will provide 90% power to detect treatment moderation by sex of magnitude 0.16 for hippocampal activation, 0.12 mm³ for hippocampal volume, and 6.63 for declarative memory (all corresponding to a medium effect size of $d = 0.68$).⁴³ We will assess treatment moderation in the same way but replacing the indicator of female sex with depressed status. Based on previous studies, a difference in declarative memory performance following CS administration between depressed people and controls has a large effect size ($d = 1.1$).⁵⁴ Using the conservative approach of powering the study for the lowest observed magnitude of $d = 0.34$ allows adequate power ($\geq 90\%$) when assessing effects with higher magnitudes.

References for sample size calculations:

Form A

IRB #	STU 2018-0360
--------------	----------------------

Form A

IRB #	STU 2018-0360
-------	---------------

Assessment Schedule

Instrument	Baseline (Visit 1)	Visit 2	Visit 3	Visit 4	Visit 5
Informed consent	X				
Medical and psychiatric history	X				
Concomitant medication review	X	X	X	X	X
Physical exam	X				
SCID-CV for DSM 5	X				
Quick Inventory of Depressive Symptomatology (QIDS-C)	X	X	X	X	X
Young Mania Rating Scale (YMRS)	X	X	X	X	X
Columbia Suicide Severity Rating Scale (C-SSRS)	X		X		X
Systematic Assessment for Treatment Emergent Event (SAFTEE)	X		X		X
Rey Auditory Verbal Learning Test (RAVLT)	X		X		X
Ruff Light Trail Learning (RULIT)	X		X		X
Volunteer Health Questionnaire	X				
Weekly Questionnaire			X	X	X
Prodromal Questionnaire – Brief Version (PQ-B)	X		X		X
Perceived Stress Scale (PSS-10)	X				
Childhood Trauma Questionnaire (CTQ)	X				
International Physical Activity Questionnaire (IPAQ)	X				
Treatment Impressions Inventory (TII)	X				
Internal Status Scale (ISS)			X		X
Blood work (CBC, CMP, morning cortisol) CMP – 8.5 mL; CBC – 4 mL; Cortisol – 10 mL	X		X		X
Blood work (GCR analysis and epigenetics, 2 x 8.5 mL)	X				
Blood work (progesterone in naturally cycling women) Progesterone – 10 mL			X		X
Blood work (Glucocorticoid)	X		X		X
Vitals	X				

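### The depression moderation (Aim 7) and the sex moderation (Aim 5) are not adjusted for each other or for age, although no balance between diagnostic groups on sex or age is stated

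*Combined protocol and SAP*

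**What the plan says.** Section 3 (Study Design): "Within each group (depressed and non-depressed), participants will be randomized to receive" hydrocortisone or placebo, with the order of the two randomised. Diagnosis is therefore a property that participants bring with them.

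Section 4.a, Aim 1, defines the treatment effect as a within-person contrast, "estimated as the within-subjects difference in hippocampal subfield activation between the hydrocortisone and placebo treatment conditions".

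Section 4.a, Aim 5, lists sex and age among the candidate moderators: "We will assess treatment moderation by sex, stress, early life adversity, age, physical activity, and changes in sleep using the modeling setup" of the primary aim. The printed equation for sex lets the treatment effect depend on the sex indicator only. It has no diagnosis term.

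Section 4.a, Aim 7: "Depression as a moderator will be assessed similarly to the moderators proposed in aim 5". The next sentence adds that "a dichotomous indicator variable representing baseline group assignment (depressed vs. healthy control) will also be included in the model". The sample-size text for Aims 5 and 7 is more explicit: "We will assess treatment moderation in the same way but replacing the indicator of female sex with depressed status". Sex is exchanged for diagnosis; the two are not kept together.

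The one figure on sex composition is in the same paragraph: "Complete data from 48 participants (50% women) will provide 90% power to detect treatment moderation by sex of magnitude 0.16". That is a power assumption, and it is not broken down by diagnosis. The documents mention no matching, quota or stratification of the two groups on sex or age. Section 1 labels Aim 7 exploratory and Aim 5 clinical.

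**The concern.** Section 1 names two group comparisons of interest: depressed against non-depressed, and male against female. Each is to be estimated as a treatment interaction that leaves the other out. Suppose the share of women differs between the diagnostic groups and women respond differently to hydrocortisone. Part of that sex difference then appears in the diagnosis-by-treatment coefficient. The same happens with age. In the other direction, if depressed people respond differently, part of that difference appears in the sex-by-treatment coefficient. A depression or sex moderation could be reported that is not there, or a real one could be hidden. Because the plan itself lists sex and age as possible modifiers of the response, this is a foreseeable source of bias.

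**Working it through.** **The plan's own moderation figure.** The stated input is 48 completers, half women, d = 0.68, 90% power. Alpha and sidedness are not stated; I take two-sided 5%.
- Plain reading, 24 v 24, with d in SDs of the within-person difference: 0.68 × √(24/2) = 2.356, and power = Φ(2.356 − 1.96) = 65%.
- With the noncentrality multiplied by √2 (for example, d on the single-measurement SD with within-person correlation 0.75): 3.331, and power = Φ(1.371) = 91.5%, close to the stated 90%.

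The figure is reproduced only under a scaling that the plan does not state. The scale of d is therefore unsettled, and I show more than one standard error below.

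**Inputs for the bias.** The 168 completers are stated as 84 per group; I assume that group means diagnosis. The true depression moderation is set to zero. A sex moderation of 0.68 is the detectable size in the sample-size text, and 0.34 is half of it. Female-share gaps of 15 and 30 points are assumed.

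**Formulas.** Spurious depression moderation = sex moderation × gap in female share. Rejection rate = P(|Z + bias/SE| > 1.96).
- SE with SD 1: √(2/84) = 0.154.
- SE implied by the plan's 90% power at d = 0.34 with 168 completers: 2 × 0.34/3.24 = 0.210.

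| Sex moderation | Gap | Bias | Rate, SE 0.154 | Rate, SE 0.210 |
|---|---|---|---|---|
| 0.34 | 15 points | 0.05 | 6.3% | 5.7% |
| 0.34 | 30 points | 0.10 | 10.1% | 7.7% |
| 0.68 | 15 points | 0.10 | 10.1% | 7.7% |
| 0.68 | 30 points | 0.20 | 26.2% | 16.3% |

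Calibrating instead to the plan's moderation statement (90% at d = 0.68 with 48, scaled to 168) gives SE = (0.68/3.24) × √(48/168) = 0.112. The 0.68 rows then become about 15% and 44%. The unsettled scale can move the rates either way.

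**Age.** A gap of 0.2 to 0.5 SD, with a response slope of 0.1 to 0.34 per SD of age (all assumed), gives a bias of 0.02 to 0.17 and a rate of 5.2% to 19.6% at SE 0.154.

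**Simulation** (10,000 runs, SD 1, sex moderation 0.68). Without adjustment, 15 and 30 points gave 9.5% and 24.2%. With a sex-by-treatment term, bias was about 0.00 and the rate 5.0% to 5.2%. Two controls confirm that both conditions are needed:
- 20 points of imbalance with a large sex main effect but no sex moderation: bias 0.00, rate 5.0%.
- Balanced sex with moderation 0.68: bias 0.00, rate 5.1%.

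**Reverse direction.** Take 65% women among the depressed and 50% among controls. The depressed share is 54.6/96.6 = 0.565 among women and 29.4/71.4 = 0.412 among men, a gap of 0.153. If the plan's d = 1.1 for memory after corticosteroids in depressed people against controls is read as a difference in response (the text does not settle this), the spurious sex moderation is 1.1 × 0.153 = 0.17.

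**The case against.** The strongest reply is that bias needs two things together, and the documents establish neither. The contrast is within-person, so groups that differ in sex or age but respond alike produce no bias, as the first simulation control shows. Aim 5 asks whether sex and age predict response; it does not assert that they do. This stands, and the point is conditional for that reason.

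A reader might take 0.68 as the sex effect that the plan expects. It is the size that 48 completers are said to detect. On the plan's raw scales it corresponds to 0.16 for activation and 0.12 mm³ for volume, which equal the whole treatment effects quoted from the earlier studies; for memory, 6.63 exceeds the quoted 4.25. The upper rates therefore rest on a large assumed moderation.

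A reader might also infer that the groups are enrolled without matching. The documents do not support that: the file has no eligibility or recruitment section and refers to a grant application that is not included. What can be said is that no balancing is stated.

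It might seem that stratifying the randomisation by sex would solve the problem. It would not. Only treatment order is randomised, and stratifying order cannot change the share of women in either diagnostic group.

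Finally, Aim 7 is exploratory. That limits how firmly its result will be read, but it does not remove a bias that the model could avoid, and the sex moderation in Aim 5 does not carry that label.

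**Conclusion.** The concern holds as a gap in the moderation models. The planned diagnosis-by-treatment estimate is open to confounding by sex and age, and the planned sex-by-treatment estimate to confounding by diagnosis and age. Whether bias occurs depends on an imbalance and on a differential response, both unknown.

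With SE 0.154, the false-positive rate for depression moderation is about 6% to 10% at a sex moderation of 0.34, and about 10% to 26% at 0.68, for gaps of 15 to 30 points. With SE 0.210 the 0.68 figures are about 8% and 16%. These rest on 84 completers per diagnostic group, two-sided 5% and no true depression moderation.

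A reader might infer that any sex or age difference between the groups would be read as a depression effect, or that the main results are in doubt. Neither follows. Main effects cancel, and the treatment effects in Aims 1–4 and 6 are unaffected.

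**What to change.** In the Aim 7 model, add sex and age as main effects and as interactions with the same condition term that carries diagnosis. In the Aim 5 sex model, add the corresponding terms for diagnosis and age. Report the depression and sex moderations from these mutually adjusted models.

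The cost is a few lines of analysis text and a few degrees of freedom out of about 168 completers. Sex and age are already needed for Aim 5, so no new data are required. For the sex term, the variance inflation of the diagnosis interaction is 1/(1 − R²), with R² = (gap²/4)/[p(1 − p)] and p the overall share of women. With 50% women in one group, a 15-point gap gives R² = 0.023 and inflation 1.02. A 30-point gap gives R² = 0.099 and inflation 1.11, and power at d = 0.68 goes from 99.3% to 98.7%.

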Aims 1, 2, 3, 4 and 6: Complete data from 168 (84 subjects per group) will provide 90% power to detect a treatment effect on hippocampal activation of magnitude 0.08 or greater (correspondingly, $d \geq 0.34$), based on the findings of Brown et al. (2013).³⁴ The magnitude of the treatment effect observed by Brown et al. (2013)³⁴ was 0.16. This is a very conservative estimate because we anticipate enrolling 188 (94 per group) expecting no more than 10% attrition. If attrition rates are abnormally high, at approximately 20%, the completer sample of 150 (75 per group) would provide 80% power and provide sufficient power to detect a statistical difference with an effect size of $d = 0.34$. Complete data from 168 (84 per group) subjects will provide 90% power to detect a treatment effect on hippocampal volume of magnitude 0.06 mm³ or greater, based on the findings of Brown et al. (2015)⁴³ and to detect a treatment effect on declarative memory of magnitude 3.31 or greater, based on the findings of Brown et al. (2013).³⁴ The magnitude of the treatment effect on hippocampal volume observed by Brown et al. (2015)⁴³ was 0.12 mm³, and the magnitude of the treatment effect on declarative memory observed by Brown et al. (2013)³⁴ was 4.25. To power the study for the spectroscopy aims, we used data from a study of patients receiving prednisone for medical illnesses vs. disease matched controls.³⁰ The participants were receiving corticosteroids for a longer duration than in the proposed study, but no studies examining more acute exposure were available. Based on the NAA/Cr values reported we expect a medium effect size ($\sim d = 0.54$). Assuming we have complete data on more than 68 (34 per group) participants we will have approximately 90% power to detect a significant difference in spectroscopy data. This is a conservative estimate given other effect sizes observed in similar work were much larger ($d = 0.84$) which would only need complete data from 40 subjects (20 per group) to observe 96% power. For clinical aim 4, complete data from 136 (68 per group) subjects will provide 90% power to detect a treatment effect on declarative memory of an effect size of $d = 0.38$ or greater, based on the findings of Brown et al. (2013).³⁴ In the case of high attrition rates ($> 28\%$) we would still have over 90% power to observe a significant effect on memory changes. Although data are not available for a sample size estimate for the exploratory aim of rsFC, a sample size of 168 (84 per group) will provide 80% power for an effect size of $d = 0.30$ which is smaller than effect sizes observed in previous work referenced above.

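### The powers given for hippocampal activation, 90% with 168 completers and 80% with 150 at the same d = 0.34, cannot both be right

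*Combined protocol and SAP*

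**What the plan says.** All the figures are in section 4.a under Sample size determination.

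- **Planned case** (the Aims 1, 2, 3, 4 and 6 paragraph): "Complete data from 168 (84 subjects per group) will provide 90% power to detect a treatment effect on hippocampal activation", for a raw effect of 0.08, equated with d of at least 0.34.
- **Enrolment** (same paragraph): "we anticipate enrolling 188 (94 per group) expecting no more than 10% attrition".
- **High-attrition case** (same paragraph, attrition about 20%): "the completer sample of 150 (75 per group) would provide 80% power and provide sufficient power to detect a statistical difference", with d = 0.34 given again.
- **Declarative memory** (same paragraph): 168 completers give 90% power "to detect a treatment effect on declarative memory of magnitude 3.31 or greater". Later, "complete data from 136 (68 per group) subjects will provide 90% power to detect a treatment effect on declarative memory" at d = 0.38.
- **Sex moderation** (the Aims 5 and 7 paragraph): "Complete data from 48 participants (50% women) will provide 90% power to detect treatment moderation by sex of magnitude 0.16 for hippocampal activation", equated with d = 0.68.

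The data analysis plan gives a single estimand for activation, the within-subject hydrocortisone-minus-placebo difference, and a single mixed model. No alpha, sidedness, SD or within-person correlation is stated, and no different test or alpha is named for the 150-completer case.

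**The concern.** The two activation statements share outcome, model and effect size; only the number of completers differs. The noncentrality of the test then grows with the square root of that number, and whatever SD or correlation lies behind d cancels from the comparison. Losing 18 of 168 completers reduces the noncentrality by about 5.5%, which is too little to take power from 90% to 80%.

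This is the plan's only statement of power for the activation aim under about 20% attrition, so it is what a reader would use to judge whether the trial tolerates heavy dropout. If the 168 figure is right, the slip is harmless. If the 150 figure is right, the headline 90% is overstated and full enrolment with no dropout would still not reach it.

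**Working it through.** **Inputs from the plan.** N = 168 at 90% and N = 150 at 80%, both at d = 0.34; 188 to be enrolled. The 150 itself is correct: 188 × 0.80 = 150.4. Only the power attached to it is in question.

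**Assumption.** Two-sided alpha 0.05, which the plan does not state; 0.01 and 0.10 are also tried.

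**1. Can the stated figures be reproduced directly?** At d = 0.34 (normal approximation):

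| Reading of the test | 168 completers | 150 completers |
|---|---|---|
| Two independent groups, 84 then 75 each | 59.6% | 54.9% |
| Paired, all completers, d in SDs of the difference | 99.3% | 98.6% |
| Paired, one group only (84 then 75) | 87.6% | 83.8% |

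No reading gives 90% and 80% together, so the check below uses scaling, which does not need the test form.

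**2. Scaling from one figure to the other.** For fixed d and alpha, power(N) = Φ(c√N − z), with z = 1.960 and c a constant. The ratio is √(150/168) = 0.9449.

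- *Keep 90% at 168.* c√168 = 1.960 + 1.282 = 3.242. At 150: 3.242 × 0.9449 = 3.063, and Φ(3.063 − 1.960) = Φ(1.103) = **86.5%**.
- *Keep 80% at 150.* c√150 = 1.960 + 0.842 = 2.802. At 168: 2.802 / 0.9449 = 2.965, and Φ(2.965 − 1.960) = Φ(1.005) = **84.3%**. Power of 90% then needs 150 × (3.242/2.802)² ≈ **200** completers.

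The noncentral t with N − 1 degrees of freedom gives the same: 86.5%, 84.3% and 200.

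**3. Could alpha or rounding explain it?** (noncentral t)

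| Condition | 150, if 90% at 168 | 168, if 80% at 150 |
|---|---|---|
| Alpha 0.01 | 85.6% | 85.2% |
| Alpha 0.05 | 86.5% | 84.3% |
| Alpha 0.10 | 86.8% | 83.8% |
| Rounding pushed to its limits (alpha 0.05) | 83.8% | 86.8% |
| One group only, 84 and 75 (alpha 0.05) | 86.4% | 84.4% |

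The rounding row lets the true d be anywhere from 0.335 to 0.345, differently at the two sample sizes, and moves the anchoring power by half a point (89.5% at 168, or 80.5% at 150). For both stated figures to hold exactly, the critical value would have to be (0.9449 × 1.282 − 0.842)/(1 − 0.9449) ≈ 6.7, a one-sided alpha of about 10⁻¹¹.

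**4. Which figure is more likely wrong?**

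*Declarative memory alone.* The paragraph on Aims 5 and 7 equates 6.63 with d = 0.68, so the SD is 6.63/0.68 = 9.75 and 3.31 is d = 0.339. Starting from 90% at 136 with d = 0.38, the noncentral t gives 89.7% at 168, agreeing with the stated 90%, and 86.1% at 150.

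*The other entries for Aims 1, 2, 3, 4 and 6.* This comparison assumes one common within-person correlation across outcomes, which the plan does not state.

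| Entry | Stated | From 90% at 168 | From 80% at 150 |
|---|---|---|---|
| Memory, 136, d = 0.38 | 90% | 90.2% | 84.6% |
| Spectroscopy, 68, d = 0.54 | about 90% | 90.1% | 84.4% |
| Spectroscopy, 40, d = 0.84 | 96% | 96.9% | 93.9% |
| Resting-state connectivity, 168, d = 0.30 | 80% | 81.6% | 74.5% |

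The first basis fits every entry within 2 points. The second misses every one.

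**5. The sex-moderation figure.** It uses the same activation scale: 0.16/0.68 = 0.08/0.34 = 0.235. Read as a contrast between two halves of 48 completers, the noncentrality is k × 0.68 × √48 / 2 with 46 degrees of freedom, where k is the constant implied by the activation figures (k × 0.34 × √N is their noncentrality). With k = 0.740 (90% at 168) power is about 40%. With k = 0.677 (80% at 150) it is about 35%. The stated 90% would need k = 1.41. So this figure fits neither basis.

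**The case against.** The best defence is that 80% is a floor. The sentence reassures the reader that power stays adequate under unusually heavy dropout, 80% is the customary threshold, and 86.5% clears it. That is plausible, but the text gives 80% as the power provided and does not mark it as a minimum, although bounds are marked elsewhere in the same section. If a floor was meant, the remedy is still an edit to that sentence.

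A second argument is that the damaging branch is the less likely one. The 90% at 168 is attached to activation, volume and memory and agrees with the neighbouring entries, whereas 80% at 150 appears once. This stands as an inference. It is not proof, because the agreement across outcomes relies on a common correlation.

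Third, the two replacement figures do not exhaust the possibilities. If d is in SDs of the within-person difference, a paired test on all completers gives about 99% at both sample sizes, and both stated figures are too low. This also stands: 86.5% and 84% are each conditional on the other stated figure being right. It does not reconcile the two figures.

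Finally, the sex-moderation figure concerns another aim, contrast and sample size, and its recomputation borrows the constant from the activation figures. It is therefore offered only as something to check, and the contradiction does not depend on it.

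**Conclusion.** The point holds. For one outcome, one test, one alpha and d = 0.34, 90% at 168 completers and 80% at 150 are incompatible by about 6 points: 86.5% at 150 if the first is right, 84.3% at 168 if the second is. The incompatibility requires only that test, alpha and d are the same in both statements. It survives two-sided alpha from 0.01 to 0.10, rounding, and a per-group reading.

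That the 80% is the likelier error, so that power is understated, is an inference from the neighbouring figures. The documents cannot confirm it without alpha, the SD that scales d and the within-person correlation. Severity is minor, since the error is probably conservative and the sample size need not change on that account.

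**What to change.** In section 4.a, Sample size determination:

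1. State alpha and sidedness, the SD that scales d, and the within-person correlation assumed for activation. Say what per group means in the crossover calculation.
2. Recompute the powers at 168 and 150 on that one basis and restate whichever fails: about 86–87% at 150 if 90% at 168 is confirmed, or about 84% at 168 if 80% at 150 is confirmed. If neither is confirmed, restate both.
3. If 80% was meant as a minimum, write 'at least 80%'.
4. Check the figure for 48 completers at d = 0.68 (Aims 5 and 7) on the same basis, since it uses the same activation scale.

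The cost is one recomputation and a short text correction. Enrolment, design and analysis are unaffected.

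### At d = 0.38, memory power cannot stay over 90% once attrition passes 28%, because the plan itself ties 90% to 136 completers (27.7% attrition)

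*Combined protocol and SAP*

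**What the plan says.** All the relevant text is in section 4.a of the combined protocol and SAP, under Sample size determination, in the paragraph on Aims 1, 2, 3, 4 and 6.

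- Enrolment: "we anticipate enrolling 188 (94 per group) expecting no more than 10% attrition".
- Clinical Aim 4: "complete data from 136 (68 per group) subjects will provide 90% power to detect a treatment effect on declarative memory", at an "effect size of $d = 0.38$ or greater".
- The next sentence takes attrition above 28% as the high-attrition case and says that "we would still have over 90% power to observe a significant effect on memory changes". It gives neither an effect size nor an upper limit on attrition.
- Earlier in the paragraph, 168 completers are said to give 90% power "to detect a treatment effect on declarative memory of magnitude 3.31 or greater". The effect seen in the earlier crossover trial is given as 4.25.
- For hippocampal activation at d = 0.34, the paragraph gives 90% power with 168 completers and 80% with 150 (about 20% attrition).

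The section does not state alpha, sidedness, or the standard deviation to which d is scaled.

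**The concern.** Two consecutive sentences conflict. If 136 completers give 90% power at a given effect size, fewer completers must give less. Attrition above 28% of 188 leaves fewer than 136, yet the second sentence puts power above 90% there.

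The sentence is the plan's reassurance about heavy dropout for one of its two clinical aims, and it is open-ended. Someone judging whether the memory analysis can still be relied on after, say, 35% or 40% dropout would take over 90% from it. The plan's own figures do not support that at d = 0.38.

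**Working it through.** **Inputs from the plan.** Enrolment 188; 136 completers for 90% power at d = 0.38; 168 completers for 90% power at d = 0.34 (memory effect 3.31); observed memory effect 4.25. **Assumption:** alpha 0.05 two-sided, since none is stated.

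**Step 1. Completers.**

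- Attrition that leaves 136: 1 − 136/188 = 27.7%, which rounds to 28%.
- Completers at 28% attrition: 188 × 0.72 = 135.4, so attrition above 28% leaves at most 135.

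**Step 2. Can the plan's 90% at 136 be reproduced?** Not exactly. With a normal approximation at d = 0.38:

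| Calculation | Power at 136 |
|---|---|
| Two-sample, 68 per group, two-sided | 60.1% |
| Paired on all 136, two-sided | 99.3% |
| Noncentrality d × √(n per group), two-sided | 88.0% |
| Same, one-sided | 93.2% |

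The third row is nearest: 0.38 × √68 = 3.134, and Φ(3.134 − 1.960) = 88.0%. It corresponds to a crossover with d scaled to the residual SD of a single period. It also comes near most of the section's other figures: 87.6% against 90% (168, d = 0.34), 88.3% against 90% (68, d = 0.54), 96.4% against 96% (40, d = 0.84) and 78.5% against 80% (168, d = 0.30). It is further off for 150 at d = 0.34 (83.8% against 80%). Rounding of d does not close the gap at 136. At d = 0.385, Φ(0.385 × √68 − 1.960) = 88.8%, and 90% would need d = 0.393.

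**Step 3. Scaling from the plan's own figure.** This takes 90% at 136 as given and lets noncentrality vary with √N. At 136 the noncentrality is 1.960 + 1.282 = 3.242, so power at N is Φ(3.242 × √(N/136) − 1.960). The last column is the nearest direct calculation from step 2, Φ(0.38 × √(N/2) − 1.960).

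| Attrition | Completers (rounded down) | Scaled from 90% at 136 | Nearest direct calculation |
|---|---|---|---|
| 27.7% | 136 | 90.0% | 88.0% |
| 28% | 135 | 89.8% | 87.7% |
| 30% | 131 | 88.9% | 86.8% |
| 35% | 122 | 86.7% | 84.3% |
| 40% | 112 | 83.7% | 81.2% |

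The scaled column is not sensitive to sidedness. With a one-sided 0.05 test the anchor is 1.645 + 1.282 = 2.927, and 112 completers give Φ(2.927 × 0.9075 − 1.645) = 84.4%.

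**Step 4. Scaling from the other anchor.** Starting from 90% at 168 and d = 0.34, noncentrality at d = 0.38 is 3.242 × (0.38/0.34) × √(N/168). Power is then 90.3% at 136, 90.1% at 135 and 89.9% at 134.

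**Step 5. If the observed effect was meant.** The plan's figures imply d = 0.34 × 4.25/3.31 = 0.437. The completers needed for 90% power are:

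- from 168 at 3.31: 168 × (3.31/4.25)² = 102, which is 1 − 102/188 = 45.7% attrition;
- from 136 at 0.38: 136 × (0.38/0.437)² = about 103, which is 45.2% attrition.

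On the nearest direct calculation, power at d = 0.437 is 94.8% at 135 completers and 90.4% at 112, so the limit lies near 40%.

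**The case against.** **The threshold is only rounding.** This stands. At 28% the gap is one completer and about 0.2 points, and on the 168-completer anchor 135 completers still give 90.1%. A reader might infer that the statement is plainly false at 28% itself, but the plan's rounded powers do not support that. It fails because it continues without limit: even on the favourable anchor, power drops below 90% at 134 completers.

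**The sentence names no effect size, and the preceding one says 0.38 or greater.** This stands in part. At the observed effect of 4.25 the claim holds well past 28%. But the text does not invoke that effect, the value attached to the Aim 4 calculation is 0.38, and a power quoted for d of 0.38 or greater is a minimum reached at 0.38. Even on the generous reading an attrition limit is needed.

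**The inequality may not be reversed.** This is fair. The 28% may simply describe what counts as high attrition. Up to about 28% is a likely intended meaning, but the documents do not settle it.

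**Paired or one-sided calculations stay above 90%.** At 135 they give 99.3% and 93.0%, but neither reproduces the plan's 90% at 136, so neither can be what lies behind the sentence.

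**Dropout is not presented as free.** A reader might infer that the plan treats heavy attrition as costless. It does not: the same paragraph shows power falling to 80% at about 20% attrition for d = 0.34.

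**Conclusion.** The statement is wrong as written, at low severity. With 188 enrolled and 90% power tied to 136 completers, power at d = 0.38 cannot be over 90% for all attrition above 28%. The shortfall is negligible at 28%, about 1 point at 30%, 3 points at 35% and 6 points at 40%. These sizes are conditional on the plan's 90% at 136, on noncentrality varying with √N, and on an assumed two-sided alpha of 0.05. The direction of the error needs only that power falls as completers fall. The 90% at 136 was not itself reproduced; the nearest direct calculation gives about 88%.

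A reader might go further and infer that the memory aim is underpowered. The documents do not support that. The plan expects no more than 10% attrition and is sized on the smaller d = 0.34. With 168 completers, scaling from 90% at 136 gives Φ(3.242 × √(168/136) − 1.960), about 95% at d = 0.38. No sample size, analysis or conclusion changes.

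**What to change.** Replace the sentence in one of two ways.

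1. Say that with attrition up to about 27.7% (at least 136 completers) power is about 90% for d = 0.38, and that it falls below 90% beyond that.
2. If another effect was meant, such as the observed 4.25, name it with its d and the attrition limit up to which power stays over 90%.

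Either way, state alpha, sidedness and the standard deviation to which d is scaled, and recheck the 90% at 136 on that basis. If power at higher attrition is quoted (about 89%, 87% and 84% at 30%, 35% and 40%), label it as conditional on the 90% at 136. The nearest direct calculation would put those figures at about 87%, 84% and 81%.

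The cost is one rewritten sentence, a short recalculation and a slightly less favourable figure.
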